4.2 Timing of analyses

The main efficacy analysis is made at 3 months and another follow-up analysis at 12 months. The primary Safety analysis will be made at 6 months.

- When locking the data at 3 months both efficacy and safety will be evaluated.
- When locking the data at 6 months only safety will be evaluated.
- When locking the data at 12 months both efficacy and safety will be evaluated.

4.3 Patient Disposition and Data Sets Analysed

The number of subjects included in each of the ITT, PP and Safety populations will be summarised. Subjects who completed the study and subjects who withdrew from study prematurely will also be presented with a breakdown of the reasons for withdrawal by treatment group for the ITT, PP and safety populations.

4.4 Protocol Deviations

Major protocol deviations are those that are considered to have an effect on the analysis. The number of patients with major protocol deviations will be summarised per treatment group. A list of protocol deviations will be produced.

4.5 Demographics and Baseline Characteristics

Demographics and baseline characteristics will be descriptively summarised by SSD and Mixed/Conductive and totally for the ITT and PP populations.

STATISTISKA KONSULTGRUPPEN		Statistical Analysis Plan	
Protocol: Clinical performance of a new implant system for bone conduction hearing		Protocol No: CBAS5539	
		Version: 1.0	Page 15 of 22

4.6 Pre operation variables

Pre operation variables will be summarised by SSD and Mixed/Conductive and totally for the ITT and PP populations and analysed according to the methods described in section “General Methodology” above.

4.7 Medical and Surgical History

Medical and surgical history, one at a time, will be summarised by CTCAE term by SSD and Mixed/Conductive and totally for ITT population.

4.8 Prior and Concomitant Medications

Prior and concomitant medication will be summarised by higher level anatomical therapeutic classification (ATC) group and generic term by SSD and Mixed/Conductive and totally for ITT population.

4.9 Concomitant Treatments/Procedures

Concomitant treatments/procedures will be listed for the ITT population. A special mark-up will be done whether to tell if the treatment was performed before or/after surgery.

4.10 Efficacy Analyses

4.10.1 Primary Efficacy Analysis

Primary efficacy analysis will be determined by analysis of change in free-field threshold audiometry: PTA4 (mean of 500, 1000, 2000 and 4000Hz) and change in Adaptive speech recognition in noise (50% performance), from unaided versus Investigational device at the 3 months visit for the ITT population, using Fisher’s one-sided non-parametric permutation test for paired observations at a significance level of 0.025 to demonstrate an improvement in PTA4. Each arm SSD and Conductive/Mixed will be tested separately. Both PTA4 and SIQ must be significant at alpha 0.025 for the primary analysis to be considered as confirmative in each arm separately. In addition, a pooled analysis for all subjects will be made.

Group mean free-field PTA4 (average of 500, 1000, 2000, and 4000 Hz) with the Osia System at the 3-month postoperative interval will be improved over that measured preoperatively in the unaided condition (baseline).

This endpoint is represented by the following hypotheses:

$$H_0: \mu_F - \alpha_0 \geq 0,$$

$$H_a: \mu_F - \alpha_0 < 0,$$

where:

α_0 = baseline preoperative PTA4;

μ_F = mean follow-up PTA4 3 months postoperative.

Group mean Adaptive speech recognition in noise (50% performance), speech to noise ratio (SNR) with the Osia System at the 3-month postoperative interval will be improved over that measured preoperatively in the unaided condition.

Protocol:

Clinical performance of a new implant system for bone conduction hearing

Protocol No:

CBAS5539

Version:

1.0

Page 16 of

22

This endpoint is represented by the following hypotheses:

$$H_0: \mu_F - \alpha_0 \geq 0,$$

$$H_a: \mu_F - \alpha_0 < 0,$$

where:

α_0 = baseline preoperative Adaptive speech recognition in noise (50% performance), speech to noise ratio (SNR);

μ_F = mean follow-up Adaptive speech recognition in noise (50% performance), speech to noise ratio (SNR) 3 months postoperative.

A sensitivity analysis of the primary variable will be done for complete cases.

The primary analyses will be performed regardless of what Osia Fitting Software version (1.0.2 OFS or 1.0.3 OFS) used at 3 months (see chapter 4.12).

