10.2.2 Secondary variables/endpoints

- Abbreviated Profile of Hearing Aid Benefit (APHAB)
- Thresholds audiometry, free-field [0.25, 0.5, 0.75, 1.0, 1.5, 2.0, 3.0, 4.0, 6.0 and 8.0 kHz]
- Speech in quiet [% correctly perceived words at 50dB, 65dB and 80dB SPL]
- Feedback measurement
- Health Utilities Index (HUI23S1EN.15Q)
- Speech, Spatial and Qualities of Hearing Scale (SSQ)
- Soft tissue thickness
- Soft tissue reduction performed
- Type of anaesthesia
- Surgery time
- Bone polishing/removal at the actuator site
- BI300 Implant length
- Location of BI300 Implant
- Surgical incision type/location
- Daily usage time
- Comfort
- Softpad use
- Choice of magnet strength
- BC Direct [0.25, 0.5, 0.75, 1.0, 1.5, 2.0, 3.0, 4.0 and 6.0 kHz]

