1.5.3 Overall sample size considerations

In order to achieve 90% power both for the primary analysis (PTA4 and SNR, Investigational Device vs. unaided) and the primary safety analysis, 50 evaluable subjects are needed. Each arm SSD and Conductive/Mixed should at least consist of 13 patients to assure a power of 90% in both arms for the primary analyses.

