3.2 Efficacy Variables/endpoints

3.2.1 Primary Efficacy Variables/endpoints

- Threshold audiometry: PTA4 (mean of 500, 1000, 2000 and 4000Hz) at visit 1 (unaided) vs 3 months post-surgery (aided).
- Change in Adaptive speech recognition in noise (50% performance) from unaided versus Investigational device at the 3 months visit.

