4 STATISTICAL METHODOLOGY

4.1 General Methodology

Since all included subjects will have measurements of the primary and important secondary efficacy variables for unaided hearing, with the Investigational device and with a Baha power sound processor on a Baha Softband, all statistical analyses will be paired. All statistical analyses will be non-parametric. In order to choose the most powerful test, the Fisher's non-parametric permutation test for paired observations will be used for all paired analyses of continuous variables. The permutation tests use the measured values and not only the ranks in the calculations. For paired analysis of dichotomous and ordered categorical variables the Sign test will be used.

The analyses will be performed in the following priority:

1. Investigational Device vs. Unaided
2. Investigational Device vs. Baha power sound processor on a Baha Softband

In addition to the change variables the distribution of all efficacy variables will be presented by visit, where applicable.

The main efficacy analysis will be performed on the ITT population and complementary efficacy analyses will be performed on the PP population. The main analysis will be performed after the 3 month visit. A complementary analysis will be performed 9 months after the main analysis (12-month visit). All significance tests will be one-sided and performed at the 2.5% significance level to demonstrate an improvement with Investigational Device.

The hierarchical testing procedure below is introduced to guarantee that the probability of Type I error is < 2.5% for all confirmative statements. The order of the hierarchical testing procedure will be:

1. PTA 4 pre-operative unaided vs 3 months (Primary efficacy analysis)
2. Adaptive speech recognition in noise (50% performance), speech to noise ratio (SNR) pre-operative unaided vs 3 months
3. Speech in quiet at 65dB SPL pre-operative unaided vs 3 months
4. APHAB Global pre-operative unaided vs 3 months aided
5. Hearing attribute (HUI-III) pre-operative unaided vs 3 months
6. Mean of the 12 items in the SSQ pre-op unaided vs 3 months

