If the first analysis is significant the probability mass 0.025 will go to the second analysis. If the second analysis is also significant the probability mass 0.025 will go to the third analysis and so on. When the first non-significant analysis is reached this and all analyses thereafter will be non-confirmative while the previous analyses will be confirmative. If the first analysis is non-significant no analysis will be confirmative.

STATISTISKA KONSULTGRUPPEN		Statistical Analysis Plan	
Protocol: Clinical performance of a new implant system for bone conduction hearing		Protocol No: CBAS5539	
		Version: 1.0	Page 14 of 22

The hierarchical testing will be made for each arm separately (SSD and Mixed/Conductive) and not totally.

We plan to analyse the similarity of the primary efficacy results among sites using non-parametric one way analyses of variance (Kruskal-Wallis test) of the difference between Unaided and ATB at 3 months. This will only be made totally and not by SSD and Mixed conductive.

Imputation of missing values will be performed for all efficacy variables. No imputation of baseline values or baseline carry forward will be made. Imputations will be made according to the following rules:

1. If a value is missing at the end of a patient, last observation will be carried forward.
2. If a missing value is occurring between two time points with values, an interpolation will be made for continuous variables and for categorical variables the value from the previous visit will be carried forward.

The distribution of continuous variables as well as change in continuous variables will be given as n, mean, SD, SEM, Median, Min and Max and the distribution of dichotomous and categorical variables will be given as number and percentages. One sided 97.5% CI will be presented where applicable.

Numbness, Adverse Events, Device deficiencies, Comfort, Usage, Surgical variables, Demographics, Baseline, Questions, Magnet strength variables will only be analysed descriptively.

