6 CHANGES OF ANALYSIS FROM PROTOCOL

No changes of the analyses according to the protocol are made.

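### The primary success sentence names an undefined endpoint (SIQ), and the SAP hierarchy gives a second, conflicting rule under which PTA4 alone can be confirmative

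*SAP*

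**What the plan says.** **The success sentence.** Protocol 10.5.1 and SAP 4.10.1 carry the same wording: "Both PTA4 and SIQ must be significant at alpha 0.025 for the primary analysis to be considered as confirmative in each arm separately". SIQ is absent from both abbreviation lists and is used nowhere else.

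**The second primary endpoint.** SAP 3.2.1 lists it as "Change in Adaptive speech recognition in noise (50% performance) from unaided versus Investigational device at the 3 months visit". Protocol 4.3 and 10.2.1, SAP 1.1, the two hypotheses written out in SAP 4.10.1, and the sample size sections agree that the pair is PTA4 and SNR.

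**Speech in quiet.** Protocol 10.2.2 lists it among the secondary endpoints as "Speech in quiet [% correctly perceived words at 50dB, 65dB and 80dB SPL".

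**The hierarchy.** SAP 4.1 adds a six-step sequence, run separately in each arm. Step 1 is "PTA 4 pre-operative unaided vs 3 months (Primary efficacy analysis"; step 2 is SNR; step 3 is "Speech in quiet at 65dB SPL pre-operative unaided vs 3 months". The stopping rule is: "When the first non-significant analysis is reached this and all analyses thereafter will be non-confirmative while the previous analyses will be confirmative".

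**Reconciliation.** The protocol contains no hierarchy. SAP section 6 states: "No changes of the analyses according to the protocol are made".

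**The concern.** There are two faults, and repairing the first does not repair the second.

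1. The sentence that decides primary success names an endpoint that is not one of the two primaries. Taken as speech in quiet, it could confirm the primary analysis when SNR failed. It could also deny confirmation when both real primaries succeeded but speech in quiet did not. It cannot be run as written either, because it does not say which of the three presentation levels counts.
2. With SIQ read as SNR, the SAP still holds two rules. SAP 4.10.1 requires both endpoints. SAP 4.1 attaches the primary label to PTA4 alone and keeps it confirmative when SNR fails.

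The study is open, with no blinding (protocol 2.2). If PTA4 is significant and SNR is not, the same data could be reported as a confirmed or an unconfirmed primary result, and the choice between the rules could be made after the results are known.

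**Working it through.** **Where the two rules differ (SIQ read as SNR)**

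| PTA4 | SNR | SAP 4.10.1: primary analysis | SAP 4.1: analysis labelled primary |
|---|---|---|---|
| significant | significant | confirmative | confirmative |
| significant | not | not confirmative | confirmative |
| not | significant | not confirmative | not confirmative |
| not | not | not confirmative | not confirmative |

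Only the second row conflicts. Steps 3-6 are unaffected, because each already needs steps 1 and 2 to pass.

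**Type I error.** A fixed sequence at one-sided 0.025 holds 0.025 per arm. Requiring both tests at 0.025 also holds it, since if either null is true the chance that both reject is at most 0.025. The issue is which claim is made, not alpha inflation.

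**Inputs** (SAP 1.5.1 and 1.5.3): one-sided alpha 0.025; power 90%; difference 10 for each endpoint; SD of change 9.5 (PTA4) and 11.3 (SNR); stated need 11 and 13 subjects; minimum 13 per arm; 50 in total. The split of the 50 between arms is not given.

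**The plan's own figures.** n = (SD × (1.960 + 1.282) / 10)², rounded up:

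- PTA4: (9.5 × 0.3242)² = 9.5, so 10
- SNR: (11.3 × 0.3242)² = 13.4, so 14

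These are close to the stated 11 and 13. The paired t-test needs 12 and 16. The plan's numbers came from simulation on data from study CBAS5675, which the documents do not include, so an exact match is not expected.

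**How often the conflicting row occurs.** Power is exact noncentral t with noncentrality (10/SD) × √n on n − 1 degrees of freedom. The correlation between endpoints is not stated, so the range runs from independence to full positive dependence:

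- independent: P(PTA4 yes, SNR no) = power(PTA4) × (1 − power(SNR))
- fully dependent: power(PTA4) − power(SNR)

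At n = 13 these are 0.9355 × 0.1666 = 0.156 and 0.9355 − 0.8334 = 0.102.

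| n in arm | PTA4 power | SNR power | Both significant | PTA4 yes, SNR no |
|---|---|---|---|---|
| 13 | 0.9355 | 0.8334 | 0.780-0.833 | 0.102-0.156 |
| 20 | 0.9938 | 0.9633 | 0.957-0.963 | 0.030-0.036 |
| 25 | 0.9990 | 0.9887 | 0.988-0.989 | 0.010-0.011 |

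At n = 37, the size of the other arm if one has 13 (50 − 13), the conflicting result has probability about 0.0005.

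**Check with the planned type of test.** A simulated sign-flip permutation test on normal data, with correlation 0 / 0.5 / 0.9, gave 0.160 / 0.141 / 0.113 at n = 13, 0.043 / 0.036 / 0.030 at n = 20 and 0.011 / 0.011 / 0.009 at n = 25.

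**If the SNR gain is smaller.** The planning data came from Mixed/Conductive subjects only, so the SSD arm has no arm-specific input. If the true SNR gain were 5 dB with the same SD (an assumption, not a figure from the documents), the conflicting result would occur in 62-64% of arms at 13, 53% at 20 and 43% at 25. With no true SNR effect, the hierarchy would still call PTA4 confirmative with probability about 0.94 at n = 13, whereas the joint rule would succeed with probability at most 0.025.

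The SIQ-versus-SNR fault cannot be sized, because the documents give no effect or SD for speech in quiet.

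**The case against.** The strongest reply has four parts.

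- **SIQ is a typing slip settled by its own paragraph.** SAP 4.10.1 names PTA4 and speech in noise and writes hypotheses for exactly those two. That is very likely right. It is still an error in the one sentence that decides success, and it was carried from the protocol into the SAP.
- **The two rules can be read together.** SAP 4.1 would govern individual endpoints and SAP 4.10.1 the overall primary verdict. SAP 4.10.2 lends some support: its secondary hypotheses within the hierarchy start with speech in quiet, which leaves SNR among the primaries. But the primary label in SAP 4.1 sits on PTA4 alone, protocol 4.2 also describes the primary assessment as PTA4, and no clause gives either section precedence. The reading is possible but not written.
- **Only one outcome is affected, and 10-16% is the worst case.** Both points stand. With 50 subjects, at most one arm can be as small as 13, and with an equal split the figure is about 1% per arm. The 5 dB figures rest on an assumption and should not carry the argument.
- **The joint rule costs no power, because it is already the written rule.** This stands against SAP 4.10.1. The loss appears only in comparison with PTA4 alone.

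**Conclusion.** The concern holds. SIQ is undefined and does not match the second primary endpoint. Once it is corrected to SNR, SAP 4.1 and SAP 4.10.1 still give opposite verdicts when PTA4 succeeds and SNR fails. On the plan's inputs this affects 10-16% of arms at 13 patients, 3-4% at 20, about 1% at 25 and under 0.1% at 37. These figures assume normal data and endpoint correlation between zero and full positive dependence. The textual fault does not depend on them: primary success needs a single definition before the data are seen, and two are written. Confidence is high, and the point must be fixed.

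**What to change.** Before the 3-month lock:

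1. In protocol 10.5.1 and SAP 4.10.1, replace SIQ with adaptive speech recognition in noise (SNR).
2. In SAP 4.1, merge steps 1 and 2 into a joint first step: PTA4 and SNR at 3 months versus unaided, each tested at one-sided 0.025 within the arm, passed only if both are significant. The present steps 3-6 follow unchanged.
3. Record the hierarchy and the joint first step in SAP section 6, in place of the statement that nothing changed.

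The alternative is to keep the six steps, delete the sentence requiring both, and state that PTA4 alone can be confirmative. It would also leave one rule, but it departs from the protocol's success criterion and is the weaker choice.

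**Cost.** This is wording only; no procedure or data collection changes. The protocol edit needs a signed amendment and the approvals described in protocol 11.3 and 12.6.1. Relative to the rule already in SAP 4.10.1 there is no loss of power. Relative to PTA4 alone, power falls from 94% to 78-83% at 13 per arm, from 99.4% to about 96% at 20, and from 99.9% to about 99% at 25.

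The SAP 1.5.3 statement, "Each arm SSD and Conductive/Mixed should at least consist of 13 patients to assure a power of 90% in both arms", should be rechecked for the joint rule on the sponsor's own simulation. By normal theory, joint power is 0.889-0.911 at 16 per arm and 0.912-0.928 at 17, so 90% needs 16-17 per arm.

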4.10.2 Secondary Efficacy Analyses

The secondary efficacy objectives in the hierarchical testing will be tested using the following hypothesis:

Group mean Speech in quiet at 65dB with the Osia System at the 3-month postoperative interval will be improved over that measured preoperatively in the unaided condition.

This endpoint is represented by the following hypotheses:

$$H_0: \mu_F - \alpha_0 \leq 0,$$

$$H_a: \mu_F - \alpha_0 > 0,$$

where:

α_0 = baseline preoperative word recognition score;

μ_F = mean follow-up word recognition score 3 months postoperative.

Group mean APHAB Global score with the Osia System at the 3-month postoperative interval will be improved over that measured preoperatively in the unaided condition.

This endpoint is represented by the following hypotheses:

$$H_0: \mu_F - \alpha_0 \geq 0,$$

$$H_a: \mu_F - \alpha_0 < 0,$$

where:

α_0 = baseline preoperative APHAB Global score;

μ_F = mean follow-up APHAB Global score 3 months postoperative.

Protocol:

Clinical performance of a new implant system for bone conduction hearing

Protocol No:

CBAS5539

Version:

1.0

Page 17 of

22

Group mean Hearing attribute (HUI-III) with the Osia System at the 3-month postoperative interval will be improved over the preoperative hearing situation.

This endpoint is represented by the following hypotheses:

$$H_0: \mu_F - \alpha_0 \leq 0,$$

$$H_a: \mu_F - \alpha_0 > 0,$$

where:

α_0 = baseline preoperative Hearing attribute (HUI-III);

μ_F = mean follow-up Hearing attribute (HUI-III) 3 months postoperative.

Group mean of the 12 items in the SSQ with the Osia System at the 3-month postoperative interval will be improved over the preoperative hearing situation.

This endpoint is represented by the following hypotheses:

$$H_0: \mu_F - \alpha_0 \leq 0,$$

$$H_a: \mu_F - \alpha_0 > 0,$$

where:

α_0 = baseline preoperative mean of the 12 items in the SSQ;

μ_F = mean follow-up mean of the 12 items in the SSQ 3 months postoperative.

Comparison regarding change from unaided hearing (if applicable) to Investigational device will be done according to the general methodology with Fisher's non-parametric permutation test for paired observations for the following variables:

- APHAB at 3, 6 and 12 months
- Threshold audiometry: PTA4 (Mean of 500, 1000, 2000 and 4000 Hz) at 4 weeks, 6 and 12 months
- Threshold audiometry: 250, 500, 1000, 2000, 3000, 4000 and 6000 Hz at 4 weeks, 3, 6, and 12 months
- Adaptive speech recognition in noise (50% performance) at 4 weeks, 3, 6 and 12 months
- Speech in quiet (50dB, 65dB and 80dB) at 4 weeks, 3, 6 and 12 months
- Feedback measurement at each frequency at 4 and 6 weeks, 3, 6 and 12 months
- HUI-III at 3, 6 and 12 months
- SSQ at 3, 6 and 12 months

Comparison of the Investigational device with a Baha Power sound processor worn on a Baha Softband will be done according to the general methodology with Fisher's non-parametric permutation test for paired observations for the following variables:

- Threshold audiometry: PTA4 (Mean of 500, 1000, 2000 and 4000 Hz) at 4 weeks, 3, 6 and 12 months
- Threshold audiometry: 250, 500, 1000, 2000, 3000, 4000 and 6000 Hz at 4 weeks, 3, 6, and 12 months

STATISTISKA KONSULTGRUPPEN		Statistical Analysis Plan	
Protocol: Clinical performance of a new implant system for bone conduction hearing		Protocol No: CBAS5539	
		Version: 1.0	Page 18 of 22

- Adaptive speech recognition in noise (50% performance) at 4 weeks, 3, 6 and 12 months
- Speech in quiet (50dB, 65dB and 80dB) at 4 weeks, 3, 6 and 12 months
- BC Direct at 4 and 6 weeks, 3, 6 and 12 months.

Choice of SP magnet and change of SP magnet. Changes in SP magnet strength will also be presented graphically in a flow graph.

All secondary efficacy analyses will be performed for both the ITT population and PP population. PTA4 will also be analysed for the PP population in the same fashion as in the primary analysis.

Analyses of Threshold Audiometry, Adaptive speech recognition in noise and Speech in quiet, BC Direct, HUI, APHAB and SSQ will be made totally and also by SSD and Conductive/Mixed patients. This will be made only for the ITT population.

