4.3 Objectives and outcome measures

| Primary objective | Outcome measure(s) |
|--|--|
| To compare hearing performance with the Investigational device and the unaided hearing situation | At 3 months 
 • Thresholds audiometry, free-field [PTA4, Mean of 0.5, 1, 2 and 4 kHz]. Investigational |

| | |
|--|---|
| | 
device (at 3 months) vs. Unaided.
 
 Adaptive speech in noise [speech-to-noise ratio, 50% speech understanding]. Investigational Device vs. Unaided (preoperative). |
|--|---|

| Secondary objective(s) | Outcome measure(s) |
|--|---|
| 
To compare hearing performance with the Investigational device and the unaided hearing situation
 | 
 Thresholds audiometry, free-field [PTA4, Mean of 0.5, 1, 2 and 4 kHz]. Investigational Device (4w, 6 and 12 months) vs. Unaided (preoperative). Thresholds audiometry, free-field [0.25, 0.5, 0.75, 1.0, 1.5, 2.0, 3.0, 4.0, 6.0 and 8.0 kHz]. Investigational Device (4w, 3, 6 and 12 months) vs. Unaided (preoperative). Adaptive speech in noise [speech-to-noise ratio, 50% speech understanding]. Investigational Device (4w, 6 and 12 months) vs. Unaided (preoperative). Speech in quiet [% correctly perceived words at 50dB, 65dB and 80dB SPL]. Investigational Device (4w, 3, 6, and 12 months) vs. Unaided (preoperative). Feedback measurements. Investigational Device (Visit 4 and onwards). |
| 
To compare the self-reported assessments of hearing outcome with the Investigational device and in a preoperative hearing situation
 | 
 Abbreviated Profile of Hearing Aid Benefit (APHAB). Investigational Device at 3 and 12 months vs. preoperative hearing situation Health Utilities Index (HUI23S1EN.15Q) at 3 and 12 months. Investigational device vs. preoperative hearing situation. Speech, Spatial and Qualities of Hearing Scale (SSQ) at 3 and 12 months. Investigational device vs. Unaided. |
| 
To collect surgical information
 | 
 Soft tissue thickness Soft tissue reduction performed Type of anaesthesia Surgery time Bone polishing/removal at the actuator site |

| | |
|--|---|
| | 
 • BI300 Implant length • Location of BI300 Implant • Surgical incision type/location |

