3.2.2 Secondary Efficacy Variables/endpoints

- Abbreviated Profile of Hearing Aid Benefit (APHAB) at visit 1 (unaided), m 3, m 6 and m 12:
 - Global score
 - Ease of Communication
 - Reverberation
 - Background Noise
 - Aversiveness
- Thresholds audiometry: PTA-4, 250, 500, 1000, 2000, 3000, 4000, and 6000 Hz at visit 1, w 4, m 3, m 6 and m 12
- Speech perception in quiet (50dB, 65dB and 80dB SPL) at visit 1, w 4, m 3, m 6 and m 12
- Adaptive speech recognition in noise (50% performance) at visit 1, w 4, m 3, m 6 and m 12
- Feedback measurement at each frequency at visit w 4, w 6, m 3, m 6 and m 12
- Generic quality of life scale: Health Utility Index (HUI) at visit 1 (unaided), m 3, m 6 and m 12:
 - Health related quality of life score for overall health
 - Vision score
 - Hearing score
 - Speech score
 - Ambulation/mobility score
 - Dexterity score
 - Self-care score
 - Emotion score
 - Cognition score
- The Speech, Spatial and Qualities of Hearing Scale (SSQ) at visit 1 (unaided), m 3, m 6 and m 12

Surgical variables

- Soft tissue thickness (mm)
- Surgery time (time of first incision to time of last suture), (min)

Protocol:

Clinical performance of a new implant system for bone conduction hearing

Protocol No:

CBAS5539

Version:

1.0

Page 12 of
22

- Type of anaesthesia
- Soft tissue thinning performed
 - Yes
 - No
- Bone polishing/removal below the actuator site performed
- BI300 length
 - 3 mm
 - 4 mm
- Location of BI300 Implant
- Surgical incision/location

Questions about usage will be collected at w 6, w 12, m 6 and m 12:

- Daily use of sound processor (hours/day)
- Softpad use
- Question about comfort with the SP, using VAS, will be collected at w 4, w 6, m 3, m 6 and m 12.
- Magnet choice will be recorded at w 4, w 6, w 12, m 6 and m 12.

BC Direct thresholds at visit 1, w 4, w 6, m 3, m 6 and m 12

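### The SAP tests APHAB, HUI and SSQ at 6 months, when the protocol does not collect them, and its interpolation rule lets the preoperative value fill gaps in aided data

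*SAP*

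**What the plan says.** SAP 3.2.2 lists "Abbreviated Profile of Hearing Aid Benefit (APHAB) at visit 1 (unaided), m 3, m 6 and m 12" as a secondary variable and gives HUI and SSQ the same four time points. SAP 4.10.2 then orders Fisher's paired permutation test for each: "APHAB at 3, 6 and 12 months", "HUI-III at 3, 6 and 12 months" and "SSQ at 3, 6 and 12 months". It adds that "All secondary efficacy analyses will be performed for both the ITT population and PP population", with further ITT analyses of these instruments by hearing-loss group.

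Protocol 4.3 defines the outcome as "Abbreviated Profile of Hearing Aid Benefit (APHAB). Investigational Device at 3 and 12 months vs. preoperative hearing situation", and HUI and SSQ likewise at 3 and 12 months. Protocol 6.5–6.7 has all three completed at Visits 1, 6 and 8. In the flow chart (Protocol 8) these are the preoperative, 3-month and 12-month visits, and Visit 7, the 6-month visit, is blank for all three. SAP 6 nevertheless states: "No changes of the analyses according to the protocol are made".

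On missing data, SAP 4.1 imputes every efficacy variable. Rule 1 carries the last observation forward at the end of a subject's record. Rule 2 interpolates a continuous value that is missing between two time points with values. Baseline is mentioned only to say that it is not itself imputed and not carried forward.

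**The concern.** There are two faults, linked by the imputation rules.

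First, the SAP orders tests at a visit with no data. The programmer must decide whether a score that was never scheduled counts as missing. If it does not, the 6-month tests cannot be run. If it does, rule 2 produces a full 6-month column, with p-values, in which no score was observed.

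Second, Visit 1 is a time point with a value, and it is measured in a different condition: unaided for audiometry, APHAB and SSQ, and in the current hearing situation for HUI (Protocol 6.7). Used as an interpolation end point, it mixes the control condition into the aided value and understates benefit. This can affect analyses such as "Threshold audiometry: PTA4 (Mean of 500, 1000, 2000 and 4000 Hz) at 4 weeks, 6 and 12 months" when the week-4 value is missing. It can also affect a 3-month questionnaire score when a 12-month score is present. Those 3-month scores are steps 4–6 of the confirmatory hierarchy. The complete-case sensitivity analysis in SAP 4.10.1 covers only the primary variable, so it would not reveal the effect on questionnaires.

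**Working it through.** **Schedules side by side**

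| Instrument | Protocol 4.3, 6.5–6.7, 8 | SAP 3.2.2, 4.10.2 |
|---|---|---|
| APHAB | Visit 1, 3 m, 12 m | Visit 1, 3 m, 6 m, 12 m |
| HUI | Visit 1, 3 m, 12 m | Visit 1, 3 m, 6 m, 12 m |
| SSQ | Visit 1, 3 m, 12 m | Visit 1, 3 m, 6 m, 12 m |

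**Tests affected.** There are four analysis sets: ITT, PP, ITT-SSD and ITT-Conductive/Mixed. 3 instruments × 4 = 12. Counting every score in SAP 3.2.2 (APHAB 5, HUI 9, SSQ 1): 15 × 4 = 60. If imputed linearly in months, each 6-month value is (12−6)/(12−3) = 2/3 of the 3-month score plus 1/3 of the 12-month score. It adds nothing to those two visits.

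**The plan's own APHAB figure.** Protocol 10.3.2 gives 28 subjects for 15 units, SD 23.3, one-sided 0.025 and 90% power. The normal approximation is (23.3 × (1.960 + 1.282)/15)² = 25.4, so 26. The paired t-test gives 28 (power 0.907), and a simulated paired permutation test at n = 28 gives about 0.90. The figure reproduces and is not in dispute.

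**Size of the anchor problem.** The SAP does not define the interpolation. Assumptions: linear in time; Visit 1 is t = 0–12 weeks before surgery; 3 months is m = 12–13 weeks; 12 months is 52 weeks; equal gain at both aided visits. Effect sizes are those in the sample-size sections (10 dB, 15 units), and the arm size is the stated minimum of 13.

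*Week-4 value missing, 3-month value present.* Share of gain kept = (4 + t)/(m + t).
- m = 13, t = 0: 4/13 = 31%, so 10 dB becomes 3.1 dB. Shortfall 6.92/13 = 0.53 dB on the arm mean.
- m = 12, t = 12: 16/24 = 67%, so 6.7 dB. Shortfall 3.33/13 = 0.26 dB.
- Assessments treated as equally spaced: 50%, so 5 dB. Shortfall 5/13 = 0.38 dB.

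*3-month APHAB missing, 12-month present.* Share kept = (m + t)/(52 + t).
- m = 12, t = 0: 12/52 = 23%, so 15 units becomes 3.5. Shortfall 11.54/13 = 0.89 units.
- m = 13, t = 12: 25/64 = 39%, so 5.9. Shortfall 9.14/13 = 0.70 units.
- Equal spacing: 50%, so 7.5. Shortfall 7.5/13 = 0.58 units.
- Visit numbers 1, 6, 8 as the scale: 5/7 = 71%, so 10.7. Shortfall 4.29/13 = 0.33 units.

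**Power for hierarchy step 4 in a 13-subject arm.** Exact sign-flip permutation test, normal differences with mean 15 and SD 23.3, 4000 runs per case (simulation error about 0.8 points):
- no gap: 55.9%
- one gap filled at 23%: 54.9%
- one gap filled at 50%: 55.7%
- that subject left out (n = 12): 53.2%

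**Can 12-month scores exist at the 3-month analysis?** Protocol 12.9 has the first subject's first visit in Q1/Q2 2017 and the last subject's in Q2/Q3 2018. With surgery 0–12 weeks after Visit 1, the first subject's 12-month visit falls between end December 2017 and September 2018. The last subject's 3-month visit falls between late June 2018 and March 2019. So they may exist. SAP 4.2 does not say whether they would be used.

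**The case against.** The schedule mismatch is conceded; the argument is about weight. The 6-month tests lie outside the hierarchy, and SAP 4.2 evaluates only safety at the 6-month lock, so the mismatch could surface only in the 12-month report. Treating a never-scheduled score as missing is a strained reading, and the 60-test count supposes that every subscore is tested. All of this stands, but the SAP still gives an instruction that cannot be followed as written.

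On the anchor, the bar on baseline carry forward suggests that the authors meant to keep Visit 1 out. Reaching steps 4–6 also needs 12-month data in the 3-month analysis, and the ordinary reading of a 3-month lock is that they are not used. In that case a missing 3-month questionnaire score simply stays missing. The 3-month PTA4 and SNR are exposed only if the week-4 value is missing too. These points limit the reach of the problem but do not close the gap in rule 2.

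The percentages rest on an interpolation scale that the SAP never defines, and 13 is the minimum arm size. With 50 subjects at least one arm has 25 or more, which roughly halves the effect per gap there. Finally, leaving the subject out costs slightly more power (53.2%) than the diluted fill. That is true, but the power kept by the fill comes from a value weighted towards the preoperative condition.

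**Conclusion.** Both parts hold. The 6-month questionnaire tests conflict with the protocol schedule, and nothing in the supplied documents reconciles them. The SAP's own flow chart page is missing from the supplied text, so the comparison rests on the protocol's schedule, which is consistent throughout. Rule 2, as written, permits a preoperative value to be blended into aided data.

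The weight is minor to moderate. The 6-month tests are non-confirmatory. The dilution is large for the subject concerned (23–71% of an APHAB gain kept, depending on the assumed scale) but small for the group: 0.33–0.89 APHAB units or 0.26–0.53 dB per gap in a 13-subject arm. It runs against the device, so it does not inflate type I error in the tests against the preoperative condition. An effect on steps 4–6 cannot be excluded, but a changed decision is unlikely.

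**What to change.** 1. Delete the 6-month time point for APHAB, HUI and SSQ from SAP 3.2.2 and 4.10.2. If a 6-month collection is really wanted, it has to be scheduled in the protocol and declared in SAP 6.
2. In SAP 4.1, allow interpolation only between two aided post-fitting values, and state that Visit 1 is never an end point.

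The cost is SAP wording only; no visit, sample size or confirmatory test changes. Some week-4 values and 3-month questionnaire scores will stay missing instead of being filled. In a 13-subject arm, one missing APHAB score then means about 53% power at step 4 instead of about 55–56%.
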